## Summary:

**Background:** One in every 15 Ethiopian children die before their fifth birthday and 7 in 10 of those deaths occur during infancy. Optimizing nutrition in young infants is one of the most effective interventions to improve infant survival and growth. In Ethiopia, only 7% of children age 6-23 months meet the minimum acceptable dietary standards and, in the Amhara region where this intervention will take place, only 3% of children under two years old get the minimum dietary diversity they need for healthy growth and development. The Amhara region is characterized by its religious tradition with 84% of the population belonging to the Ethiopian Orthodox faith tradition. Partnerships with faith leaders may provide a culturally relevant platform for accessing women and infants, increasing uptake of practices known to improve infant health and development, and providing support for women in the postnatal period and throughout the first year of their child's life.

**Objective:** The study aims to determine the impact of a behavior change intervention that partners Orthodox priests with members of the Health Development Army (HDA) and trains them to conduct newborn health outreach to increase rates of early initiation of exclusive breastfeeding through 6 months and vaccination coverage at six months. We will also determine the impact of the intervention on infant growth at between 5 and 6 months of age, observed and self-reported changes in nutrition and feeding practices of mother and infants, and early identification of newborn illness.

**Methods:** The study utilizes a community-randomized trial design in which 11 communities will be randomized to receive the intervention and 11 communities will be randomized as control communities. The unit of randomization at the house of worship. The target population for this undertaking is pregnant women and women who recently delivered in rural communities in the North Gondar region of Ethiopia. Infants enrolled in the study will have a baseline evaluation within 10 days of birth and the primary outcomes of mid-upper arm circumference (MUAC) and exclusive breastfeeding will be measured at a follow-up visit at between 5 and 6 months after birth. The sample size of 150 infants from intervention churches and 150 infants from control churches is based on identifying a statistically significant difference of  $\geq 0.2$  cm in mid-upper arm circumference (MUAC) with 80% power at  $\alpha=0.05$ , anticipating 20% of participants being lost to follow-up. We will also have 80% power to detect a significant difference of 50% exclusive breastfeeding at 5-months in the control group versus 70% in the intervention group.

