## Study Objectives:

The **primary objective** of the study is to determine the impact of a behavior change intervention that partners Orthodox priests with members of the Health Development Army (HDA) and trains them to conduct newborn health outreach to increase rates of early initiation of and exclusive breastfeeding through 6 months and vaccination coverage at 6 months.

Secondary objectives include:

- Determine the impact of the intervention on infant growth at six months, observed and self-reported changes in nutrition and feeding practices of mother and infants, and early identification of newborn illness.
- Design a culturally relevant, scalable intervention for community-based newborn and infant health in Gondar in partnership with local partners, the Federal Ministry of Health, and the Gondar Regional Health Bureau.

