The trained priests and HDA members will be dispatched to their respective communities to begin the intervention. Their primary activities will be identification of near-term pregnant and newly delivered women, providing health education to their families, follow-up visits to enable newborn-mother pairs to access child health care services, and to provide health education at religious and community gatherings. Specifically, pre-planned visits of parishioners' families will be done by the respective priests and the partnering HDA members during the last month of pregnancy, immediately after the delivery of the baby and around the time of baptism for the newborn. These visits will be used to educate pregnant and postpartum women and their families on newborn health topics including initiation of breastfeeding, duration of breastfeeding/ exclusive breastfeeding, vaccination, cord care, and utilization of available newborn health care services. These community-based activities will be monitored through regular follow-up visits by the UoG study team and discussions with priests and HDA members.

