### **Prospective follow-up**

Research assistants will work for the zonal health office to identify all births occurring in the study area. Independent of the intervention outreach teams, the research assistants will attempt to contact all newborn-mother pairs within 10-days of birth. Most contacts will occur at home, but contact may be made at other locations (e.g., health facility, church). Mothers will be invited to participate in the study, and each participating newborn-mother pair will be followed-up by the study team for up to 6 months after enrollment.

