## **Statistical analysis plan**

We will compare infant outcomes between children exposed to the intervention and those in control communities. We will use logistic regression to compare dichotomous outcomes (e.g., exclusive breastfeeding through 6 months, completion of vaccinations, infant hospitalization) and linear regression for continuous outcomes (e.g., mid-upper arm circumference). Primary outcomes will be evaluated using an intention-to-treat analysis without adjustment for other covariates. We will account for correlation within church communities by adjusting the variance for the effect of clustering.

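### Primary MUAC may be read at any age in a one-month window and is compared without age, so a gap between arms in mean visit age would pass straight into the effect estimate; a target age and an age term remove this cheaply.

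*Combined protocol and SAP*

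**What the plan says.** The Methods paragraph of the Summary states that MUAC and exclusive breastfeeding "will be measured at a follow-up visit at between 5 and 6 months after birth". The Objective paragraph of the Summary gives the same interval for infant growth. The secondary objective under Study Objectives is worded differently: "Determine the impact of the intervention on infant growth at six months". No section sets a target day or a tolerance around one.

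The Statistical analysis plan uses linear regression for MUAC, with the variance adjusted for clustering by church community, and adds: "Primary outcomes will be evaluated using an intention-to-treat analysis without adjustment for other covariates". The Data Collection section does not list infant age at the visit among the predictors (the list is open-ended), and no MUAC-for-age score is named.

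On scheduling, the Data Collection section has the University of Gondar team visiting both intervention and control communities to enrol pairs, arrange follow-up and collect data. The Procedures section has follow-up visits arranged once baseline data are collected. Up to three study visits are planned and anthropometry is taken on routine visits, but the Summary ties the primary value to a single follow-up visit.

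**The concern.** MUAC is expected to rise with age in early infancy, so a reading at 5.0 months and one at 6.0 months are not interchangeable. Here they are pooled as raw values. Visit age is settled by field scheduling after allocation, so randomisation does not guarantee that it balances. If one arm were seen systematically earlier, its mean MUAC would be lower for that reason alone, and the planned model could not separate this from the intervention effect.

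The second primary outcome would move the other way. Continuing exclusive breastfeeding can only fall with age, so the arm seen earlier would look better on breastfeeding and worse on MUAC. The two primary results would then be hard to read together. With a target difference of only 0.2 cm, even a modest gap in mean age is worth closing off in advance.

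**Working it through.** **Inputs from the documents.** "The sample size of 150 infants from intervention churches and 150 infants from control churches"; target difference 0.2 cm; power 80%; alpha 0.05 (taken as two-sided, since sidedness is not stated); 20% loss to follow-up; 11 communities per arm; visit window of about one month.

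**Assumed input.** MUAC gain of 0.1 to 0.3 cm per month at this age. The documents give no growth rate.

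**The plan's own figure.** 120/(1 − 0.20) = 150 per arm, and 2 × 120 = 240 agrees with the number of completers under Number of Subjects. The 120 itself cannot be reproduced, because no MUAC standard deviation or intracluster correlation is given. It can only be back-solved:

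- Standard error implied by the power statement: 0.2/(1.960 + 0.842) = 0.0714 cm. This needs no standard deviation or intracluster correlation, provided the design does deliver 80% power.
- Standard deviation implied with no design effect: 0.0714/√(2/120) = 0.553 cm.

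**Step 1: equal age spread in both arms.** For visit ages uniform over one month, the added SD is g/√12, where g is the gain per month. Total SD = √(0.553² + g²/12).

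| Gain (cm/month) | Added SD (cm) | Total SD (cm) | Power |
|---|---|---|---|
| 0.1 | 0.029 | 0.554 | 79.9% |
| 0.2 | 0.058 | 0.556 | 79.6% |
| 0.3 | 0.087 | 0.560 | 79.0% |

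The width of the window alone costs one point of power at most.

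**Step 2: a gap between arms in mean age.** Bias b = g × days/30.44. With SE = 0.0714:

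- Type I error = Φ(−1.960 + b/SE) + Φ(−1.960 − b/SE)
- Power with a true 0.2 cm effect and opposing bias = Φ((0.2 − b)/SE − 1.960)

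For a 7-day gap:

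| Gain (cm/month) | Bias (cm) | Share of 0.2 cm | Type I error | Power if bias opposes |
|---|---|---|---|---|
| 0.1 | 0.023 | 11% | 6.2% | 69.8% |
| 0.2 | 0.046 | 23% | 9.9% | 57.8% |
| 0.3 | 0.069 | 34% | 16.2% | 45.0% |

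Worked for the middle row: b = 0.2 × 7/30.44 = 0.046 and b/SE = 0.644. Type I error = Φ(−1.316) + Φ(−2.604) = 0.099. Power = Φ(2.157 − 1.960) = 0.578.

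**Step 3: the gap needed to reach half the target.** Days = (0.1/g) × 30.44, which is about 30, 15 and 10 days at 0.1, 0.2 and 0.3 cm per month. That is between a third and all of the window.

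**Step 4: what chance alone would produce.** The SD of a uniform one-month age is 1/√12 = 0.289 months. If infants are timed independently, the SE of the difference in mean age is 0.289 × √(2/120) = 0.037 months, about 1.1 days. If all infants in a community were seen at the same age, it is 0.289 × √(2/11) = 0.123 months, about 3.7 days. A 7-day gap would therefore be unusual without some systematic cause.

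**The case against.** The strongest reply is that nothing in the documents points to different timing by arm. One team works in both arms, follow-up is arranged in the same way for every pair, procedures are standardised with an on-site manager, and research assistants contact mothers independently of the outreach teams. Chance variation in visit age between communities is between-cluster variation, which the clustering adjustment is meant to absorb. An unadjusted primary analysis is a legitimate prespecified choice, and it does not bar supporting analyses that use age. All of this stands. It limits the point to a risk the plan leaves open.

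Three stronger readings are tempting, and the text does not carry them.

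- A reader might infer an arm-specific mechanism from the Study Design section, where of the priest and Health Development Army outreach it says: "These community-based activities will be monitored through regular follow-up visits by the UoG study team". That sentence concerns supervision of the outreach. It does not say that outcome visits are timed by those trips, or in which direction they would shift.
- A reader might infer a window wider than a month from Prospective follow-up: "each participating newborn-mother pair will be followed-up by the study team for up to 6 months after enrollment". That is a maximum length of follow-up, not a time at which MUAC is read. Both statements in the Summary give 5 to 6 months.
- A reader might take an extreme case as the headline. A 15-day gap at 0.3 cm per month gives 0.3 × 15/30.4 = 0.148 cm, or 74% of the target. In a window of about 30 days with visits spread evenly, that would need, for example, one arm seen entirely in the first half and the other entirely in the second. Nothing in the documents suggests this.

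What survives the objection is that the stated primary model offers no protection if timing does drift, and that choosing age adjustment after seeing an imbalance would be open to challenge as post hoc.

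**Conclusion.** The point holds as a cheap improvement. The primary MUAC reading may fall anywhere between 5 and 6 months, one objective words the time differently, and the primary model contains no age term, so a between-arm gap in mean visit age would become bias one for one. No such gap is shown or predicted by the documents, and without one the loss is negligible.

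Conditional on a 7-day gap, the bias is 0.023 to 0.069 cm, or 11% to 34% of the target. At 0.2 cm per month, type I error is about 10%, or power about 58%. These figures rest on an assumed growth rate, an assumed gap, a two-sided test, and the 0.0714 cm standard error implied by the stated power. If the true standard error is larger, the same bias distorts the test less.

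**What to change.** - **Summary and Study Objectives:** reconcile the wording to one target age for the outcome visit, counted from date of birth, with one stated window for both arms.
- **Data Collection:** state that the visit date is recorded. Date of birth is named under Data Security Protections; visit date is not named anywhere, although tablet capture makes it easy to hold.
- **Statistical analysis plan:** prespecify exact age in days at measurement as a linear term in the primary MUAC model, and in a sensitivity analysis of exclusive breastfeeding.
- **Reporting:** give age at the outcome visit by arm.

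The cost is wording and one recorded date. The small downside is that the primary MUAC model is no longer strictly unadjusted and uses one extra parameter. Precision does not suffer: if the implied 0.553 cm SD already includes one month of age spread, removing that spread gives power of 80.1% to 81.0% over the assumed growth range, using SD = √(0.553² − g²/12).

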**Number of Subjects:**

Group name/description	Desired number of individuals (or other subject unit) who will complete the research
Newborn/Mother Pairs	240

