**Procedures:**

The intervention in this study is intimately tied to the cultural customs and values of the North Gondar region of Ethiopia. In this region, religious leaders of the Orthodox Church have the potential to be strong advocates or hindrances to effort to improve public health and this study aims to explore how linking religious leaders to frontline health workers may catalyze and empower local communities to improve health outcomes for newborns. The study engages several experienced Ethiopian investigators and will seek continual input from a Steering Committee of community members in Gondar to ensure that all elements of the study are culturally appropriate and conducive to the local context.

Newborn-mother pairs will be recruited within the first 10 days after delivery as reported to the study team by Health Extension Workers (HEWs) engaged in the study. Recruitment will start one month following the start of the intervention and all reported newborn-mother pairs who meet the screening criteria will be included in the study until the calculated sample sizes are reached. HEW's routine registers of new deliveries will be used to trace, recruit and screen study participants. Newborn-mother pairs who fulfill an initial screening criteria will be reported to the study team at the University of Gondar (UoG) who will travel to the study site regularly for recruitment of study participants and data collection. Newborn-mother pairs will be reported to the UoG study team both through phone calls made by HEWs and in-person at the time of regular onsite visits by the team.

Eligible newborn-mother pairs will be visited by a member of the study team at their home or at an appointed meeting location in their community to complete the verbal informed consent process. Those pairs who attend church at a parish that received the intervention will be assigned to the intervention arm, and those from the parishes where no intervention was conducted will be assigned to the control arm. Initial baseline data will then be collected and follow-up visit schedules arranged with the study team.

The following materials will be used during the recruitment of study participants:

- Oral consent scripts (see attached scripts) will be used to provide information about the study to potential subjects.
- A checklist of the initial screening criteria will be used by the HEWs and study team to identify appropriate newborn-mother pairs.

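### Does the 80% power claimed for both primary outcomes fail because no ICC, design effect or MUAC SD is given for the 11 v 11 churches?

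*Combined protocol and SAP*

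**What the plan says.** The Summary (Methods) describes a "community-randomized trial design in which 11 communities will be randomized to receive the intervention" and 11 to serve as controls, with the house of worship as the unit of randomisation. In the same paragraph, "The sample size of 150 infants from intervention churches and 150 infants from control churches is based on identifying a statistically significant difference" of at least 0.2 "cm in mid-upper arm circumference (MUAC) with 80% power at" a significance level of 0.05, with 20% loss to follow-up expected. Breastfeeding is then added at that sample size: "We will also have 80% power to detect a significant difference of 50% exclusive breastfeeding at 5-months in the control group", against 70% in the intervention group.

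The Number of Subjects table gives 240 pairs under "Desired number of individuals (or other subject unit) who will complete the research". The Procedures section states no number per church: "all reported newborn-mother pairs who meet the screening criteria will be included in the study until the calculated sample sizes are reached". On clustering, the Statistical analysis plan says: "We will account for correlation within church communities by adjusting the variance for the effect of clustering".

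None of the supplied text gives a MUAC SD, an ICC, a design effect, an assumption about variation in church size, or the sidedness of the test.

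**The concern.** Infants from the same church are likely to resemble each other, so 120 evaluable infants in 11 churches carry less information than 120 independent infants. The planned analysis allows for this in the variance, so its power depends on the ICC and, for MUAC, on the SD. The power statement names loss to follow-up as its only allowance. It reads like a calculation for individually randomised infants placed in a cluster trial.

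If so, both primary outcomes could be less well powered than stated. Recruitment without a per-church number could make church sizes uneven, which lowers power further. The worry would be a trial too small for its targets, and a null result that readers could not weigh against 0.2 cm or 50% v 70%.

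**Working it through.** **Inputs from the documents.** 150 enrolled per arm, 20% loss, 11 churches per arm, alpha 0.05, MUAC difference 0.2 cm, breastfeeding 50% v 70%.

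**Assumptions.** Two-sided test, normal quantiles (1.960 and 0.842, sum 2.802) and equal church sizes, unless stated otherwise.

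1. *Evaluable numbers.* 0.8 × 150 = 120 per arm, which agrees with 240/2. Mean church size is m = 120/11 = 10.91.

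2. *Breastfeeding, no clustering.* The unpooled variance term is 0.5 × 0.5 + 0.7 × 0.3 = 0.46; the pooled term is 2 × 0.6 × 0.4 = 0.48.
   - Unpooled: 0.2/√(0.46/120) = 3.230, and 3.230 − 1.960 = 1.270, so power is 89.8%.
   - Pooled: (0.2 − 1.960 × √(0.48/120))/√(0.46/120) = 1.228, so power is 89.0%.
   - For exactly 80%, 93 (pooled) or 90.3 (unpooled) per arm are enough. The pooled figure means enrolling 93/0.8, or 117, against the planned 150.

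3. *Clustering that breastfeeding can absorb.* The design effect is DE = 1 + (m − 1) × ICC.
   - Pooled: DE = 120/93 = 1.29, so ICC = 0.29/9.91 = 0.029.
   - Unpooled: DE = 120/90.3 = 1.33, so ICC = 0.33/9.91 = 0.033.

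4. *MUAC.* The stated figure cannot be reproduced without an SD, but the condition for 80% can be found: SD × √DE ≤ 0.2/(2.802 × √(2/120)) = 0.553 cm. At the design effects in step 3 this means an SD of 0.553/√1.29 = 0.487 cm or 0.553/√1.33 = 0.480 cm. One modest design effect with an SD near 0.48 cm therefore gives both 80% figures.

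5. *Power over a range of ICCs.* The ICCs and the SD of 0.50 cm are illustrative and do not come from the documents.

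| ICC | DE | Breastfeeding power | Largest MUAC SD for 80% | MUAC power at SD 0.50 cm |
|---|---|---|---|---|
| 0.01 | 1.10 | 86–87% | 0.527 cm | 84% |
| 0.02 | 1.20 | 83–84% | 0.505 cm | 81% |
| 0.05 | 1.50 | 74–75% | 0.452 cm | 72% |
| 0.10 | 1.99 | 61–63% | 0.392 cm | 59% |

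6. *Sensitivity of the limits.*
   - A t reference with 20 df (22 churches − 2) lowers the breastfeeding ICC limit to about 0.020 (unpooled variance) and the MUAC bound to 0.526 cm.
   - An assumed coefficient of variation of 0.5 in church size lowers the ICC limit to 0.023–0.026 (normal) or 0.016 (t).
   - A one-sided alpha raises the limits to about 0.065 and 0.62 cm.
   - The plan commits to none of these.

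7. *What a null result would show.* At ICC 0.05 the 95% half-width for breastfeeding is 1.960 × √(0.46 × 1.495/120) = 0.148, or about 15 percentage points. For MUAC at SD 0.50 cm it is 1.960 × 0.50 × √(2 × 1.495/120) = 0.155 cm. An estimate near zero would then exclude 20 points or 0.2 cm. With a larger ICC or SD the interval widens and shows openly that the result is inconclusive. Neither reading needs the planning ICC.

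**The case for a change.** The strongest case for a change is that an MUAC difference has no power figure without an SD, and that a cluster trial should state its ICC. Both points are true, and the basis for 150 per arm cannot be checked. The margin is also limited. At ICC 0.05 breastfeeding power is 74 to 75% (71% with 20 df). MUAC has no slack unless the SD is below 0.553 cm: at an assumed SD of 0.8 cm, power would be 49% even with no clustering. Stating the inputs would cost only wording.

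What stands is that the inputs are missing. What does not stand is that a stated figure is wrong. No text supports an ICC of 0.05 over 0.02, or an SD of 0.8 cm over 0.48 cm. The one claim that can be tested leans mildly the other way: ignoring clustering gives 89 to 90% for breastfeeding, while the plan claims 80%. That gap is about what a modest clustering allowance would leave. It does not prove that one was made, since the sample size rests on MUAC and the breastfeeding figure may simply mean at least 80%.

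The argument about null results fails, because the clustering-adjusted interval answers it directly.

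**Conclusion.** No change to the plan is needed. The 80% figures are conditional on unstated inputs, but they are attainable and not contradicted. With 120 evaluable per arm, two-sided 0.05, normal quantiles and equal church sizes, 80% holds for breastfeeding up to an ICC of about 0.03, and for MUAC when SD × √DE is at most 0.553 cm. Whether the true values fall inside those limits cannot be settled from the documents, in either direction.

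The omission affects only the ability to audit the planning statement. It does not alter enrolment, the estimates or the validity of the primary analysis, because an analyst following the SAP will already allow for church-level correlation. A sponsor who holds the SD and ICC could usefully record them, but nothing in the conduct or analysis depends on it.
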